### **15.1 Data Collection and Processing**

This study will utilize a (Case Report Form) CRFs. All data requested on the CRFs are considered required. Data points not collected and/or recorded will be considered deviations unless otherwise specified.

The Principal Investigator must ensure the accuracy and completeness of the recorded data and then provide his/her signature on the appropriate CRFs and will be documented in compliance with local regulations. Changes to data previously submitted to the sponsor will require a new signature by the Investigator to acknowledge/approve the changes.

Visual and/or computer data review will be performed to identify possible data discrepancies. Manual and/or automatic queries will be created and will be issued to the site for appropriate response. The site staff will be responsible for resolving all queries in the database.

## **16.0 Study Supplies and Device Accountability**

### **16.1 Packaging**

The Pure Vu disposables are composed of biocompatible plastic parts and are supplied clean in a sealed package. The shelf life of the device was tested within the device verification and validation process to support shelf life period of 9 months.

### **16.2 Labeling**

All equipment associated with the clinical trial will be identified with visible markings stating "Exclusively for clinical investigation only".

All packages are labeled in conformance to Motus GI Packaging Best Practice, which are applicable to Single Use, Limited Shelf Life, Lot produced items. Examples of the main system

Document title:	Document No.	Version	Page 41 of 61
Optimizing the Preparation Regime Prior to Colonoscopy Procedure with Pure-Vu System	CL00042	1.0	

and packaging label as well as operation instructions, precautions and warnings are defined in the “Instructions For Use”.

### **16.3 Inventory Control**

The sponsor will initiate shipment of the product from the sponsor to the site upon receiving all required documents (e.g., approval/favorable opinion from IRB). The sponsor will maintain tracking for all shipment documentation. Prior to any shipment, the site will be informed by the sponsor of the upcoming shipment, expected arrival date, and content of the shipment. The site should confirm receipt of the shipment. The site will file the Sponsor’s Shipping Receipt in the Sponsor’s Study File.

An Investigator’s Device Accountability form will be conducted under the Regulatory Binder at each site and will be monitored by the site’s clinical research associate (CRA).

In case of technical failure, the site will approach the technical support team which will help solve the problem and will notify the site’s CRA.

For each dispensed Pure-Vu Oversleeve, the following information should be recorded:

- The subject study number
- Date dispensed
- Disposables' ID number

At the termination of the study, all unused study material must be returned with the corresponding documentation as directed by Motus GI.

### **16.4 Retention of Records**

All source documents and CRFs will be kept for a period of no less than five years after the later of the following dates: the date of which the study is terminated or completed or; the date that the records are no longer required supporting marketing applications.

### **16.5 Study Completion/Termination of Study**

Motus GI reserves the right to discontinue the study at any stage, with suitable written notice to all investigators and reviewing IRBs, following unforeseen events or other factors that do not permit continuation of the study. Similarly, investigators may withdraw from the study at any time, subject to providing written notification to Motus GI 30 days prior to the date they intend CL00042/ Protocol, Version 1.0 December 13, 17

CONFIDENTIAL

Document title:	Document No.	Version	Page 42 of 61
Optimizing the Preparation Regime Prior to Colonoscopy Procedure with Pure-Vu System	CL00042	1.0	

to withdraw. However, Motus GI and investigators will be bound by their obligation to complete the follow-up of subjects already participating in the study. The subjects must be followed according to the clinical protocol, and information obtained during subject follow-up shall be reported to Motus on the appropriate eCRF.

The appropriate ethics committees will be notified of discontinuation of the trial for any reason not later than 5 working days after the sponsor makes this determination and not later than 15 days after the sponsor receives a notice from the ethics committee and/or regulatory authority.

## 19.0 Appendixes A: Study Design and Schedule of Assessment

Visit	Visit 1	Colon Preparation	Visit 2	Contact
Days	>-5 days	-1 to 0 days	0	48 hours
Informed Consent*	X			
Eligibility assessment (medical records, BMI, etc.)	X			
Randomization	X			
Colon Preparation Instructions	X			
Medical History, Concomitant Medications, Demographic details	X			
Diaries	X (providing)	X (by the patients)		
Patients' satisfaction questionnaire	X (providing)	X	X	
Bowel Preparation		X (by the patients)		
Colonoscopy Procedure			X	
Follow Up			X	X
Adverse Events Reporting			X	

Document title:	Document No.	Version	Page 45 of 61
Optimizing the Preparation Regime Prior to Colonoscopy Procedure with Pure-Vu System	CL00042	1.0	

[figure not shown]

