## 7.2 Anticipated Risks Associated with bowel preparation agents

The Bowel preparation agent used in this study are approved in U.S.

The main anticipated risks associated with the bowel preparation agents including nausea with or without vomiting, abdominal pain and dehydration.

The preparation in this study is less intensive compared to the standard preparation done prior to colonoscopy procedure, thus we expect that the risks related to the preparation agent will be similar or even lower than the risks following a standard preparation to colonoscopy procedure.

Reduction of the bowel preparation regimen will minimize patient discomfort and AEs associated with bowel cleansing, and potentially maximize the efficacy of the colonoscopy procedure with Pure-Vu System.

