#### **11.1.2 Randomization**

Randomization in blocks will be applied for each site to allocate patients to one of two different bowel preparation regimens (Prep A versus Prep B). The study will utilize randomization in blocks using the standard envelope procedure, which will be applied in order to allocate patients into two arms:

- Group 1 - Will go through the Prep A procedure
- Group 2 - Will go through the Prep B procedure

The site randomization plan will be provided to the study coordinator prior the study start. No blinding is applicable in this study.

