#### **11.1.3 Screen Failures**

A subject is considered enrolled in the study when the ICF is signed. Only subjects who receive study-assigned procedures will be followed. Subjects who provide study consent, but then are determined to be ineligible prior to randomization will be considered screening failures and will

Document title:	Document No.	Version	Page 27 of 61
Optimizing the Preparation Regime Prior to Colonoscopy Procedure with Pure-Vu System	CL00042	1.0	

not require additional study follow-up. The reason for the screening failure will be clearly documented, the Subject "Enrollment and Visit Log" will be completed and the subject eligibility section in visit 1 as well as a "Study Completion" form will be completed in the CRF.

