## 12.4 Effectiveness Analyses

### Safety Analysis

The secondary endpoint is to evaluate the Device related adverse event and the overall adverse events rate. The safety analysis set will consist of all patients who were enrolled into the study.

Individual listings of adverse events including type of device, adverse events (reported term), seriousness, duration, relationship to the study device, severity and the adverse events outcome will be provided for the total population and per study arm. AEs will be summarized using frequency counts and percentages per study arm.

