### 13.1 Adverse Event (AE)

An AE is any untoward medical occurrence, unintended disease or injury, or untoward clinical signs (including abnormal laboratory findings) in subjects, whether or not related to the investigational medical device.

This definition includes events related to the investigational medical device or the comparator and the procedures involved.

AEs will be collected starting from the time subject is enrolled until the follow-up period is completed.

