**Report Serious Adverse Event (SAE) within 48 hours of learning the event**

Adverse Event (AE) Form	Please Check
Have any AEs occurred during the study?	Yes / No
If yes,	
Start Date	__ / __ / __ DD MM YY
End Date	__ / __ / __ DD MM YY
Description:	
 
• Tissue trauma
 
• Excessive bleeding
 
• Laceration
 
• Other: _____
 
• Death
 

Severity	
 
• Mild
 
• Moderate
 
• Severe
 

Anticipated	Yes / No
Relation to the study	
 
• Unrelated
 
• Unlikely
 
• Possibly
 
• Related
 

Was the AE serious AE?	Yes / No
If yes, specify the reason	
 
• Death
 
• Life threatening
 
• Hospitalization
 
• Persistence / significant disability / incapacity
 
• Congenital anomaly / birth defect
 
• Important medical event (subject's health is at risk and intervention is required to prevent one of the above events) , specify
 

Document title:  Optimizing the Preparation Regime Prior to Colonoscopy Procedure with Pure-Vu System	Document No.  CL00042	Version  1.0	Page 61 of 61
---	-----------------------------	--------------------	------------------

	Date of Event report to the IRB:  ____ / ____ / ____ DD MM YY
Treatment?	Yes / No
If yes, specify type and reason	Pharmacological treatment  _____
	Other medical intervention  _____
Outcomes	

• Resolve

• Improved

• Unchanged

• Worsen

• Insufficient follow up

• Comments: _____

Investigator signature	_____
Date	____ / ____ / ____ DD MM YY

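### The schedule marks adverse event reporting at Visit 2 only, against section 13.1, and no step explicitly asks about adverse events during the preparation days

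*Protocol*

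**What the plan says.** Section 13.1 sets the window for adverse events (AEs): "AEs will be collected starting from the time subject is enrolled until the follow-up period is completed". Section 11.1.3 fixes the start of that window: "A subject is considered enrolled in the study when the ICF is signed". Consent is obtained at Visit 1, before any preparation. Sections 9.0 and 11.1.5 have AEs captured at the phone call after the procedure.

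The schedule in Appendix A has four columns: Visit 1, Colon Preparation, Visit 2 and the 48-hour Contact. As the table was extracted, the row "Adverse Events Reporting" carries one mark, under Visit 2.

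On the preparation itself, section 7.2 states: "The main anticipated risks associated with the bowel preparation agents including nausea with or without vomiting, abdominal pain and dehydration". Section 5.1 lists comparing AE rates after the two preparations among the study objectives. Section 12.4 adds: "AEs will be summarized using frequency counts and percentages per study arm".

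**The concern.** Both arms have the same device and the same procedure; only the bowel preparation is randomised. Any true difference in AEs between arms should therefore come mainly from the preparation, and the events named in section 7.2 can occur at home before Visit 2.

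A site that works from Appendix A sees no AE mark for that period and none at the phone call. If nobody puts the question, a preparation-phase event may be recorded for one subject and missed for another, depending on who mentions it and who asks. The per-arm AE table would then be least dependable where the arms can differ. An event not asked about at the time cannot be reliably recovered at analysis.

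**Working it through.** The plan states no figure on this point, so the check sets the passages side by side.

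**Step 1: schedule against text**

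| Period | Within the section 13.1 window? | AE row in Appendix A | Other text |
|---|---|---|---|
| Visit 1, after consent | Yes | Blank | Section 11.1.3: enrolment is signature of the consent form |
| Colon Preparation | Yes | Blank | Section 7.2 names the expected events |
| Visit 2 | Yes | Marked | – |
| 48-hour Contact | Yes | Blank | Sections 9.0 and 11.1.5 capture AEs at the call |

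The row is marked in 1 of 4 columns; the section 13.1 window touches all 4. The schedule and the text disagree.

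**Step 2: does any instrument ask about AEs in the preparation days?**

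- Visit 2 pre-examination list (section 11.1.5): covers eligibility and consent, diary collection, background data, device checks and the rectal exam. It has no AE question.
- Diary (Appendix D): the logs shown cover food, liquids and bowel movements. There is no symptom field.
- Follow-up call (section 11.1.5): checks for a change in well-being after the procedure and documents any AE. It does not point back to the preparation.
- AE form (Appendix F): asks whether any AE occurred during the study, so its period does include the preparation. Its named descriptions are "Tissue trauma", excessive bleeding, laceration and death. A preparation symptom goes under the open field.
- Patient questionnaire (Appendix E): before the procedure it rates how tolerable the diet and the purgative were, and the disruption caused. It yields no event term, date, seriousness or relationship.

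So the preparation is asked about, but its AEs are not explicitly asked about.

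**Step 3: subjects who do not complete the preparation**

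- Section 11.1.5: they do not have the procedure and are excluded from the study.
- Section 11.1.3: only subjects who receive study-assigned procedures are followed.
- Section 12.5: everyone who undergoes bowel preparation is in the safety analysis. Section 12.4 uses everyone enrolled. Under either definition, those who started the preparation are counted.

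These subjects are therefore in the safety denominator, with no stated step that obtains their AEs. Intolerance is a plausible reason for stopping, so this is where a missed event is most likely to matter.

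**The case against.** The strongest reply is that the governing text is right. Section 13.1 sets the full window, section 13.10 requires every observed AE on the case report form whatever its relationship to the device, and section 10.4 trains sites in AE reporting. The AE form's question covers the whole study, and an AE report at Visit 2 can look back over the preparation. Tolerability is also measured separately with prompts, and section 12.4 compares patient satisfaction between arms. All of this stands, and it limits the point to a risk. It does not set a moment or a prompt for asking about symptoms at home, and a tolerability rating is not an AE record.

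A reader might infer that preparation-phase AEs will be under-recorded, that nothing at Visit 2 touches the preparation, or that the two preparations will falsely look equally tolerated. The documents support none of these. The duty to record is stated, the questionnaire and diary both deal with the preparation, and the AE table is not the only evidence on tolerability. A reader might also take the single marked column to mean that only one day is covered. That confuses the day on which the question is asked with the period that it can cover.

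Three cautions on reading apply. The table was read from PDF, and a merged AE cell cannot be ruled out. The neighbouring follow-up row shows separate marks for Visit 2 and Contact, which speaks against a merged cell. The questionnaire row, however, is blank at Contact although some of its questions are answered by phone, so the table may be loosely drawn or shifted. Second, section 11.1.4 describes the diary more broadly than the logs shown, and the numbering of Appendix D skips 22.4. Third, the follow-up sentence in section 11.1.3 sits under screen failures and could be read to include the assigned preparation; the exclusion in section 11.1.5 would then need to be squared with it.

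Finally, the safety objective in section 8.2 concerns the device, so device-type terms plus an open field on the AE form are not an error.

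**Conclusion.** The point holds as an inconsistency with a practical consequence. The Appendix A row, as extracted, contradicts sections 13.1, 9.0 and 11.1.5. Separately, no Visit 2 step or diary field shown asks explicitly about AEs in the preparation days, although AE rates are to be compared between the two preparations. The consequence is a risk of incomplete and inconsistent recording of preparation-phase AEs, greatest among subjects who do not complete the preparation.

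No numerical size can be given, because the protocol states neither expected AE rates nor the share of events reported without a prompt. Randomisation is blocked within site, so differences in site habit should not by themselves favour an arm; the damage would be mainly to the completeness of the AE data.

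The schedule contradiction rests on the extracted table and should be checked against the original page. The missing question does not depend on the table. It rests on the Visit 2 list and on the diary logs shown in Appendix D.

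**What to change.** 1. In Appendix A, mark the AE row from consent at Visit 1 through Colon Preparation and Visit 2 to the phone Contact, matching section 13.1.
2. In the Visit 2 pre-examination list of section 11.1.5, add one standard question, put to every subject before the procedure, on AEs since consent. It should mention the risks named in section 7.2.
3. State that the same question is put to subjects who start but do not complete the preparation, and reconcile this with the exclusion in section 11.1.5 and the follow-up sentence in section 11.1.3.

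A symptom line in the diary and preparation terms on the AE form are optional; they are a choice between prompted and open elicitation.

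The cost is a minor amendment: one table row, one checklist line and one sentence. Recorded AE rates will look higher than without the question, and the report should say that they were solicited.

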## 20.0 Appendixes B: Bowel Preparation flow chart

### 20.1 Appendixes B1: Bowel Preparation for morning procedures

[figure not shown]
Document title:	Document No.	Version	Page 46 of 61
Optimizing the Preparation Regime Prior to Colonoscopy Procedure with Pure-Vu System	CL00042	1.0	

## 20.2 Appendixes B2: Bowel Preparation for afternoon procedures

Document title:	Document No.	Version	Page 47 of 61
Optimizing the Preparation Regime Prior to Colonoscopy Procedure with Pure-Vu System	CL00042	1.0	

## 21.0 Appendixes C: Boston Bowel Preparation Scale

- ❖ **A:** Score 0- Unprepared colon segment with mucosa not seen due to solid stool that cannot be cleared.
- ❖ **B:** Score 1 - A portion of the mucosa of the colon segment is seen, but other areas of the colon segment are not seen well due to staining, residual stool, and/or opaque liquid.
- ❖ **C:** Score 2- A minor amount of residual staining, small fragments of stool, and/or opaque liquid are visible, but the mucosa of the colon segment are seen well.
- ❖ **D:** Score 3- The entire mucosa of the colon segment is seen well with no residual staining, small fragments of stool, or opaque liquid.

Document title:	Document No.	Version	Page 48 of 61
Optimizing the Preparation Regime Prior to Colonoscopy Procedure with Pure-Vu System	CL00042	1.0	

## 22.0 Appendix D – Patient Diary

### 22.1 Diet Instructions for morning procedures

**No Seeds or Nuts 5 day before your procedure**

***Drink at least two liters of CLEAR LIQUIDS per day beginning at 2 days prior to your procedure***

**On the day before your Procedure You Can Eat the Following:**

Breakfast	 20 oz of clear liquid  1-2 slices of white bread + cheese spread/ cottage cheese/ butter/ margarine/ 1 Tablespoon of mayonnaise/ honey  1 plain yogurt/sour cream  Scrambled eggs ( 1-2 eggs)  Tea sweetened with white sugar or coffee added with a small amount of milk/cream
Lunch	 20 oz of clear liquid  1-2 slices of white bread with cheese spread, butter, margarine, honey.  4-6 oz of chicken soup containing skinless chicken, peeled potato, no vegetables.  Pasta or noodles with butter (no red sauce) or white rice
Dinner	 20 oz of clear liquid  1-2 slices of white bread + cheese spread/ cottage cheese/ butter/ margarine/ 1 Tablespoon of mayonnaise/ honey  1 plain yogurt/sour cream  Pasta or noodles with butter (no red sauce) or white rice  Clear chicken soup  Tea sweetened with white sugar or coffee added with a small amount of milk/cream

**On the procedure day:**

Clear-liquid diet up to 3 hours prior to the procedure

Fasting (no food / liquids) start 3 hours prior to procedure time

Document title:	Document No.	Version	Page 49 of 61
Optimizing the Preparation Regime Prior to Colonoscopy Procedure with Pure-Vu System	CL00042	1.0	

## 22.2 Diet Instructions for afternoon procedures

No Seeds or Nuts 5 day before your procedure

***Drink at least two liters of CLEAR LIQUIDS per day beginning at 2 days prior to your procedure***

On the day before your Procedure You Can Eat the Following:

Breakfast	 20 oz of clear liquid  1-2 slices of white bread + cheese spread/ cottage cheese/ butter/ margarine/ 1 Tablespoon of mayonnaise/ honey  1 plain yogurt/sour cream  Scrambled eggs ( 1-2 eggs)  Tea sweetened with white sugar or coffee added with a small amount of milk
Lunch	 20 oz of clear liquid  1-2 slices of white bread with cheese spread, butter, margarine, honey.  4-6 oz of chicken soup containing skinless chicken and peeled potato.  Pasta or noodles with butter (no red sauce) or white rice
Dinner	 20 oz of clear liquid  1-2 slices of white bread + cheese spread/ cottage cheese/ butter/ margarine/ 1 Tablespoon of mayonnaise/ honey  1 plain yogurt/sour cream  Pasta or noodles with butter (no red sauce) or white rice  Clear chicken soup  Tea sweetened with white sugar or coffee added with a small amount of milk

On the day of your Procedure You Can Eat a light breakfast as the Following:

Breakfast	 20 oz of clear liquid  1-2 slices of white bread + cheese spread/ cottage cheese/ butter/ margarine/ 1 Tablespoon of mayonnaise/ honey  1 plain yogurt/sour cream  Tea sweetened with white sugar or coffee without milk/cream
------------------	--

Clear-liquid diet up to 3 hours prior to the procedure

Fasting (no food / liquids) start 3 hours prior to procedure time

Document title:  Optimizing the Preparation Regime Prior to Colonoscopy Procedure with Pure-Vu System	Document No.  CL00042	Version  1.0	Page 50 of 61
---	------------------------------------	---------------------------	------------------

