### 3.0 Protocol Synopsis

Study Summary					
Study Purpose	To determine the optimal bowel preparation regimen for Pure-Vu System procedures in patients indicate for colonoscopy procedure.				
Objective	The primary objective of this multicenter, prospective, randomized study is to evaluate the performance of Pure-Vu System in cleansing patients' colon who are indicated for a colonoscopy procedure using one of two different reduce bowel preparation regimes.in addition, the cecum intubation rate, time to cecum, total procedure time, and adverse event will be evaluated.				
Test and Comparator Procedures	Prep A	Prep B			
5 days prior procedure day					
No seedy food					
1 day prior procedure day					
Low residue diet;					
Spilt dose of 15 oz Magnesium Citrate + 39 oz of clear liquid		Spilt dose of 10 oz Magnesium Citrate + 32oz of clear liquid			
Procedure Day					
Clear-liquid diet up to 3 hours prior to the procedure					
Fasting (no food / liquids) start 3 hours prior to procedure time					
*At least 2 liter water per day during the preparation days.					

Document title:  Optimizing the Preparation Regime Prior to Colonoscopy Procedure with Pure-Vu System	Document No.  CL00042	Version  1.0	Page 8 of 61
---	------------------------------------	---------------------------	-----------------

Protocol Number	CL00042
Protocol Title	Optimizing the Preparation Regime Prior to Colonoscopy Procedure with Pure-Vu System Rev 1.0
Study Sponsor	Motus GI Medical Technologies, [name] [contact] [contact]
Sponsor Representative	[name] Director of Clinical Affairs
Study Type	Multicenter, prospective, randomized feasibility study
Study Product	Pure-Vu System
Study Phase	Post-market
IDE Number	K173392 Class II
Study Location	United States
Study Duration	Study period will last approx. 12 months
Study Design	Patients will be randomized to receive one of two bowel preparation regimens prior to colonoscopy with Pure-Vu procedure.
Planned Follow-Up	Telephone follow-up will be conducted at 2-3 working days post-procedure to assess subject well-being and capture any adverse events.
Subject Population	Subjects indicate for colonoscopy procedure

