## 6.3 Clinical data to Date

The latest Pure-Vu System tested in ninety-seven subjects (54% males) from five sites using similar protocol.

Pure-Vu was used in subjects with a partially prepped receiving a colonoscopy for screening, diagnostic or surveillance.

To ensure an inadequately prepped colon subjects underwent a reduced preparation consisting of dietary restrictions (no dried fruit, seeds or nuts) starting 2 days prior to the colonoscopy, an 18 to 24 hour clear liquid diet and a split dose of 20mg Bisacodyl.

The cleansing quality was evaluated before and after use of the Pure-Vu System with the Boston Bowel Preparation Score (BBPS) (1).

Two patients were excluded from the analysis due to the followings:

Document title:	Document No.	Version	Page 18 of 61
Optimizing the Preparation Regime Prior to Colonoscopy Procedure with Pure-Vu System	CL00042	1.0	

- One patient who had breakfast on day of procedure was excluded from the cleansing efficacy and usability analysis due to non-compliance with the pre-procedural prep regimen.
- In one patients the device could not reach beyond the sigmoid colon due to the patient's anatomy, thus the physician used a slim colonoscope to complete the procedure and indicated that only a slim colonoscope would be able to advance past the sigmoid and into the cecum.

The Pure-Vu significantly increased the number of subjects with an adequate cleansing level (BBPS  $\geq 2$  for all 3 colon segments) from 25%; CI 95% [17%, 35%] at baseline to 99%; CI 95% [94%, 100%] after Pure-Vu. Cecum intubation rate was 98%; CI 95% [94%, 100%]). Mean post-treatment BBPS score was  $8.7 \pm 1.0$  vs.  $3.9 \pm 2.2$  prior to Pure-Vu use. Physicians were satisfied with the device's use. No major difficulties were experienced when performing polypectomy and no serious adverse events were reported.

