### 10.3 Withdrawal Criteria

Subjects may withdraw from the study at their own request or at the request of their legally acceptable representative. The investigator may withdraw a subject from the study at any time for the following reasons:

- Severe side effects clearly related to the study device.
- Presence or appearance of exclusion criteria.
- Appearance of accompanying diseases rendering further participation in the study impossible.
- A significant protocol violation, as determined either by the sponsor or the investigator
- Subject noncompliant with investigational procedures
- Subject noncompliant with visits
- At the specific reasonable request of the sponsor

The sponsor must be informed in each withdrawal case. The reason for withdrawal must be recorded in the CRF and in the patient file.

Document title:	Document No.	Version	Page 25 of 61
Optimizing the Preparation Regime Prior to Colonoscopy Procedure with Pure-Vu System	CL00042	1.0	

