#### **11.1.4 Colon Preparation**

Subjects will be instructed to follow a detailed dietary and colon preparation regimen prior to the procedure day. All colon preparation products will be standard colon cleansing products approved by the FDA.

Patients will be randomized to one of two bowel preparation regimens (instruction for bowel preparation for morning and afternoon procedures are provided in appendix B1 and B2).

Subjects will keep a timed diary of key preparation steps and bowel activity, in addition questions about the patients satisfaction from the bowel preparation regime and diet instruction will be captured (Appendix D).

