#### **11.1.5 Colonoscopy procedure (Visit 2)**

##### Pre-Examination Procedures

- Verify eligibility checked and informed consent was obtained after explaining all risks, benefits, and alternatives to the candidate.
- Verify that the research assistant has collected completed diaries from the subject.
- Verify all background/clinical information, demographic and medical history was documented

Note: Subjects that did not take the bowel preparation or failed to complete the bowel preparation will not undergo the procedure and will be excluded from the study.

- Verify all connections and assembles are properly attached (see Instructions for Use)
- Verify device works properly (see Instructions for Use)
- Place and prepare the subject for the procedure as per standard colonoscopy.
- Perform a digital rectal exam as per standard colonoscopy, evaluate the adequate level of the preparation and start the colonoscopy procedure with the Pure-Vu System as per standard of care.

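### The synopsis and the patient diary give different procedure-day diets for afternoon procedures, so the dietary part of the regimen, and compliance with it, is contradictory for those subjects

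*Protocol*

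**What the plan says.** The Protocol Synopsis (section 3.0, Test and Comparator Procedures) sets out the two regimens. Its procedure-day rows are shared by both arms and make no distinction by time of day: "Clear-liquid diet up to 3 hours prior to the procedure" and "Fasting (no food / liquids) start 3 hours prior to procedure time".

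Appendix D gives the patient separate instructions by slot. Section 22.1 (morning) repeats the two synopsis lines and adds no procedure-day meal. Section 22.2 (afternoon) says "On the day of your Procedure You Can Eat a light breakfast as the Following". The items include "1-2 slices of white bread + cheese spread/ cottage cheese/ butter/ margarine/ 1 Tablespoon of mayonnaise/ honey" and a yogurt or sour cream. The same clear-liquid and fasting lines then follow.

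Section 11.1.4 does foresee slot-specific instructions: "instruction for bowel preparation for morning and afternoon procedures are provided in appendix B1 and B2". The Appendix B flow charts are not shown in the text available for this review.

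Three provisions attach consequences to compliance. Section 10.3 lists "Subject noncompliant with investigational procedures" among the reasons for which the investigator may withdraw a subject. Section 11.1.5 states: "Subjects that did not take the bowel preparation or failed to complete the bowel preparation will not undergo the procedure and will be excluded". Section 12.5 removes cases withdrawn before the Pure-Vu procedure from the efficacy analysis.

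**The concern.** The trial compares bowel preparation regimens, and the synopsis makes the procedure-day diet part of each regimen. For afternoon subjects that part exists in two versions, and one of them allows solid food on the day the colon is scored.

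Two things are at stake. The first is description: a report that takes the regimen from the synopsis would misstate what afternoon subjects were told to do, and the per-arm rates of adequate cleansing would be attached to the wrong diet. The BBPS is scored on insertion and again on withdrawal, so what was eaten that morning may plausibly bear on it. The second is the analysis set: if one site works from the synopsis and another from the diary, the same breakfast could be noncompliance at the first and compliance at the second. Withdrawal before the procedure removes a subject from the efficacy analysis.

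**Working it through.** The plan gives no figure to reproduce on this point. The check is a comparison of texts, followed by tracing the consequence through the compliance rules.

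**Step 1: procedure-day intake, by source**

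| Source | Applies to | Solid food that day | Final 3 hours |
|---|---|---|---|
| Synopsis, 3.0 | All subjects, both arms | None; clear liquids only | Nothing by mouth |
| Appendix D, 22.1 | Morning procedures | None; clear liquids only | Nothing by mouth |
| Appendix D, 22.2 | Afternoon procedures | Light breakfast allowed | Nothing by mouth |
| Appendix B1 and B2 | Morning and afternoon | Not visible | Not visible |

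The first two rows agree. The third differs from the first in one respect, the breakfast. The fasting window is the same in every visible source.

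**Step 2: is there an order of precedence?** Sections 9.0, 11.1.1 and 11.1.4 send the reader to Appendix B for instructions. None of them says that the synopsis line has an afternoon exception, or that the appendices override it.

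**Step 3: what happens to an afternoon subject who eats the breakfast?** Under section 22.2 the subject has complied; under section 3.0 the subject has not.

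- Section 10.3 permits withdrawal for noncompliance but does not require it.
- Section 11.1.5 bars from the procedure anyone who did not complete the bowel preparation, without saying whether diet is part of completing it.
- Appendix F records completion for the 10 oz or 15 oz magnesium citrate only. That suggests completion means the purgative, but no text says so.
- Section 12.5 then drops subjects withdrawn before the procedure from the efficacy analysis.

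Exclusion is therefore possible under the wording, not prescribed by it.

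**Step 4: does the conflict separate the arms?** Magnesium citrate is 15 oz for Prep A and 10 oz for Prep B in the synopsis, and Appendix F carries the same two volumes. The diet text is shared by both arms, and section 11.1.2 allocates in blocks within site. The two diet versions therefore fall on both arms alike in expectation.

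**Step 5: how many subjects?** Number affected = share of afternoon procedures × share of those who eat the optional breakfast × N. N is up to 100, and neither share is stated. With each anywhere from 0 to 1, the range is 0 × 100 = 0 to 1 × 1 × 100 = 100. The documents do not narrow it.

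**Step 6: is the information captured?** The log in section 22.3 has a breakfast food entry for the day of the procedure, diaries are collected before the examination (section 11.1.5), and Appendix F records the colonoscopy start time. Food and slot can both be recovered from existing forms.

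**The case against.** The strongest reply is that a synopsis summarises, that the body of the protocol expressly provides for separate morning and afternoon instructions, and that Appendix B2 may state the breakfast exactly as the diary does. The afternoon page can also be read as a sequence: breakfast, then clear liquids, then the fast. The diary is what the patient holds, so withdrawing someone for following it would require a site to put a synopsis line above the patient's own instructions. Much of this stands. It makes an intended afternoon exception plausible and wrongful exclusion less likely. It does not remove the error, because the synopsis would still misstate the regimen for afternoon subjects, and nothing visible tells a site which text governs.

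A reader might infer more than the documents support:

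- *That the preparations under test are undefined.* They are not. The volumes that distinguish the arms are consistent; only the dietary component conflicts.
- *That the comparison between arms is biased.* The diet is common to both randomised arms, so the conflict does not by itself favour either.
- *That a procedure-day breakfast is already noncompliance in this programme.* Section 6.3 does report that "One patient who had breakfast on day of procedure was excluded from the cleansing efficacy and usability analysis". That study used another preparation, with an 18 to 24 hour clear-liquid diet and bisacodyl, so its exclusion sets no rule here.
- *That the instructions conflict on fasting before the procedure.* The three-hour fast is identical in the synopsis and both diary pages.
- *That a particular number of patients is affected.* Any such count would rest on an assumed share of afternoon procedures, and the breakfast is permitted, not required.

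**Conclusion.** Wrong as written, and minor. For afternoon procedures the synopsis and Appendix D contradict each other on whether solid food is allowed on the procedure day. The contradiction affects the stated regimen, the interpretation of the per-arm adequacy rates, and the possibility that a subject who followed the diary is treated as noncompliant and lost from the efficacy analysis.

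Its effect on those rates cannot be sized from the documents: the number of subjects concerned lies between 0 and 100, and nothing is given on how a light breakfast changes the BBPS after cleansing. The conclusion rests on the visible text. Appendix B2 could confirm either version, but it could not make the synopsis and the diary agree. No judgement is made on which diet rule is correct.

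**What to change.** Reconcile section 3.0 with Appendix D, and check Appendix B2 against both, so that procedure-day intake is stated identically everywhere by morning or afternoon slot. The sponsor must decide which version is intended.

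Add two sentences on compliance: one stating that following the reconciled instruction for the subject's slot counts as compliance for section 10.3, and one stating whether diet counts towards completing the preparation in section 11.1.5.

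The cost is a few lines of wording, best agreed before sites begin to apply the exclusion rules. No new food or slot field is needed, since the diary log and the colonoscopy start time already hold that information.
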